#### 8.2.4 Test article control (Test 4):

- a. A [REDACTED] aliquot of the test or control article will be inoculated with a volume of the challenge microorganism so that the resulting suspension contains [REDACTED] CFU/mL in the same manner as Test 1.
- b. Within one min the microorganisms will be enumerated (in triplicate) by standard microbiological methods extant in the laboratory.
- c. Duplicate [REDACTED] aliquots will be removed and plated using TSA pour plates.
- d. After 30 minutes, the microorganisms will be enumerated a second time using the same procedures.
- e. Duplicate [REDACTED] aliquots will be removed and plated using TSA pour plates.
- f. This procedure will be repeated two times for a total of three replicates.

8.3. Incubation:

All plates for Tests 1, 2, 3 and 4 will be incubated for  $48\pm2$  hours at  $35^\circ\pm2^\circ\text{C}$ .

8.4. Interpretation of data:

- a. The number of surviving challenge microorganisms for each replicate from each test will be average count of the three plates.
- b. The number of survivor values will be transformed to  $\log_{10}$ .
- c. The number of survivors ( $\log_{10}$ ) from each test (1, 2, and 4) will be compared to the test microorganism viability population (test 3).
- d. Neutralization aspects of the sampling solution will be considered adequate if the mean  $\log_{10}$  CFU/mL of Test 1 is not more than 0.20  $\log_{10}$  less than the mean  $\log_{10}$  CFU/mL of Test 3 (Mean  $\log_{10}$  CFU/mL from Test 3 – Mean  $\log_{10}$  CFU/mL from Test 1 using corresponding time points).
- e. The sampling solution will be considered non-toxic if the mean  $\log_{10}$  CFU/mL of Test 2 is not more than 0.20  $\log_{10}$  less than the mean  $\log_{10}$  CFU/mL of Test 3 (Mean  $\log_{10}$  CFU/mL from Test 3 – Mean  $\log_{10}$  CFU/mL from Test 2 using corresponding time points).
- f. The mean  $\log_{10}$  CFU/mL from Test 4 must be at least 0.20  $\log_{10}$  less than the mean  $\log_{10}$  CFU/mL of Test 3.
- g. The amount of CFU added for each aspect must be confirmed to yield a final suspension containing [REDACTED]/mL (validated in test 3).
- h. The sterility controls must be negative for growth.

8.5. Controls:

8.5.1 Sterility control:

Triplicate plates of TSA and TSA+N used will be incubated with the test. In addition, triplicate [REDACTED] aliquots of sampling solution and PBW will be plated using TSA pour plates used for a particular test date. All plates will be incubated with the test.

8.5.2 Challenge microorganism confirmation:

In order to confirm growth consistent with the challenge microorganism, Gram stains will be performed from a representative colony from a test plate. The colony morphology will be noted as well.

#### 14.11 Skin Irritation Rating Scale

Skin Irritation Rating Scale Reactive area(s) within the treatment site only		
Condition	Rating	Description
Erythema	0	No reaction
	1	Mild and/or transient redness
	2	Moderate redness
	3 a	Severe redness
Edema	0	No reaction
	1	Mild and/or transient swelling
	2	Moderate swelling
	3 a	Severe swelling
Rash	0	No reaction
	1	Mild and/or transient rash
	2	Moderate rash
	3 a	Severe rash
Dryness	0	No reaction
	1	Mild and/or transient dryness
	2	Moderate dryness
	3 a	Severe dryness

a = A rating of 3 on the skin irritation scale in any category will be recorded as Adverse Event and will require subject's removal from the study.

**14.12 Estimation of Sample Size Report**

See attached report.

**14.13 Informed Consent Forms**

See attached forms

Date Issued: 07/13/16 [REDACTED]	Laboratory Project Identification No. 865-105 Zurex Pharma, Inc. Project No.: ZX-ZP-0073		
STUDY TITLE: Pivotal Clinical Evaluation to Characterize the in vivo Effects of Topically Applied ZuraPrep™ [REDACTED]	STUDY DIRECTOR: M. [name] CCRP Signature [REDACTED] Date 07/13/16		
TEST AND CONTROL ARTICLES: ZuraPrep™ ZuraPrep™ Vehicle [REDACTED] ChloraPrep® 1 [REDACTED] (Scrub Teal® Tint)	ID/LOT NO. Pending Pending Pending Pending	DATE RECEIVED: Pending Pending Pending Pending	DS NO. Pending Pending Pending Pending
PERFORMING DEPARTMENT(S): Clinical Laboratory	STORAGE CONDITIONS: Location: Pending ■ Dark ■ Ambient Room Temperature □ Desiccator □ Freezer □ Refrigerator □ Other:		
PROTECTIVE PRECAUTION REQUIRED: MSDS ■ Yes □ No			
PHYSICAL DESCRIPTION: □ Solid ■ Liquid □ Aerosol ■ Other: Liquid-filled and empty applicators			
PURPOSE: See attached protocol. AUTHORIZATION: See client signature.			
PROPOSED EXPERIMENTAL START DATE: 07/29/16 TERMINATION DATE: 12/31/16			
CONDUCT OF STUDY: ■ FDA □ EPA □ R&D □ GLP ■ GCP □ Other:			
SPONSOR: Zurex Pharma, Inc. [REDACTED] Middleton, WI [REDACTED]	CONTACT PERSON: [REDACTED] Telephone No. [REDACTED] Electronic mail [REDACTED]		
TEST CONDITIONS:			
Challenge organism(s):	[REDACTED]		
Active ingredient(s):	ZuraPrep™: Isopropyl Alcohol (~70 %) ChloraPrep® [REDACTED] (Scrub Teal® Tint): 2% Chlorhexidine Gluconate (w/v) and 70% isopropyl alcohol (v/v)		
Neutralizer(s):	Sampling solution, sterile [75mM phosphate buffer ([REDACTED]) containing [REDACTED] lecithin, [REDACTED] Tween® 80, and [REDACTED] Tamol, [REDACTED]		
Application Time(s):	30 seconds scrub followed by 3 minutes dry time for the abdomen and a 2 minutes scrub followed by 3 minutes dry time for the groin.		
Contact Time(s):	30 seconds $\pm$ 5 seconds, 10 minutes $\pm$ 30 seconds and 6 hours $\pm$ 30 minutes		
Contact Temperature(s):	Ambient room temperature		
Incubation Time(s):	72 $\pm$ 4 hours (test)	48 $\pm$ 2 hours For NE Validation	
Incubation Temperature(s):	30 $\pm$ 2C (test)	35 $\pm$ 2C For NE Validation	
Comments: A minimum of 352 subjects will be treated bilaterally using the investigational study products, one positive control product and one negative control product to yield 320 readings each for the investigational study product and positive control product and 64 readings for negative control product for each of the two test sites (abdominal and inguinal regions).			

Date Issued: 07/13/16 [REDACTED]

Laboratory Project Identification No. 865-105  
Zurex Pharma, Inc. Project No.: ZX-ZP-0073

**Protocol Amendment(s):**

[figure not shown]
1. This amendment is made to clarify the Section 7 of Appendix 14.10 of the protocol.

A: For each side of the body, mark the abdominal test areas using a sterile 2" x 5" template. The 2" x 5" areas will be delineated with each containing two 1" x 1" sampling sites.

B: Using the scrub cup technique at approximately 30 seconds post-prep, begin collecting samples from each of two sampling sites within each test area using SS by two technicians simultaneously.

Date Issued: 08/02/16 [REDACTED]	Laboratory Project Identification No. 865-105 Zurex Pharma, Inc. Project No.: ZX-ZP-0073		
STUDY TITLE: Pivotal Clinical Evaluation to Characterize the in vivo Effects of Topically Applied ZuraPrep™ [REDACTED]	STUDY DIRECTOR: M. [name] CCRP Signature [REDACTED] 08/02/16 Date		
TEST AND CONTROL ARTICLES: ZuraPrep™ [REDACTED] ZuraPrep™ Vehicle (Without Isopropyl Alcohol) [REDACTED] ChloraPrep® [REDACTED] (Scrub Teal® Tint)	ID/LOT NO. [REDACTED]	DATE RECEIVED: [REDACTED]	DS NO. [REDACTED]
PERFORMING DEPARTMENT(S): Clinical Laboratory	STORAGE CONDITIONS: Location: [REDACTED] ■ Dark ■ Ambient Room Temperature □ Desiccator □ Freezer □ Refrigerator □ Other:		
CONDUCT OF STUDY: ■ FDA □ EPA □ R&D □ GLP ■ GCP □ Other:			
SPONSOR: Zurex Pharma, Inc. [REDACTED] Middleton, WI [REDACTED]	CONTACT PERSON: [REDACTED] Telephone No. Electronic mail		
Protocol Amendment(s):			

2. This amendment is issued to clarify the last paragraph of section 3.3 on page 9 of the protocol. The last paragraph should read "Subjects will be identified by their initials, a screening ID number, and a subject number. Subject numbers will not be assigned until a subject has passed the screening criteria, including baseline bacterial counts (at least <math>1.0 \times 10^5</math> CFU/cm^2 in the groin and at least <math>1.0 \times 10^3</math> CFU/cm^2 on the abdomen). Subjects whose abdominal and groin regions qualify will be assigned the subject number. Therefore, each of the participating subjects will be assigned two identification numbers: screening identification number and a subject number".
 
3. This amendment is issued to correct the typographical errors and clarify third paragraph of section 4 on page 16 of the protocol should read "Subjects who are treated but discovered to have Treatment Day baseline counts below the minimum values or above the maximum values stated in Table 3.2 will not be included in the primary efficacy analysis for the body site(s) that did not meet the Treatment Day baseline criteria".
 
4. This amendment is issued to update the "Pending" Test and Control Article Information. The required information outlined above.
			
[REDACTED]			

Date Issued: 08/17/16 [REDACTED]	Laboratory Project Identification No. 865-105 Zurex Pharma, Inc. Project No.: ZX-ZP-0073		
STUDY TITLE: Pivotal Clinical Evaluation the Antimicrobial Effectiveness of Topically Applied ZuraPrep™	STUDY DIRECTOR: M. [name] CCRP _____ Signature [REDACTED] Date 08/17/16		
TEST AND CONTROL ARTICLES: ZuraPrep™ [REDACTED] ZuraPrep™ Vehicle (Without Isopropyl Alcohol) [REDACTED] ChloraPrep® [REDACTED] (Scrub Teal® Tint)	ID/LOT NO. [REDACTED]	DATE RECEIVED: [REDACTED]	DS NO. [REDACTED]
PERFORMING DEPARTMENT(S): Clinical Laboratory	STORAGE CONDITIONS: Location: [REDACTED]  Dark  Ambient Room Temperature  Desiccator   Freezer  Refrigerator  Other:		
CONDUCT OF STUDY:  FDA  EPA  R&D  GLP  GCP  Other: SPONSOR: Zurex Pharma, Inc. [REDACTED] Middleton, WI [REDACTED]	CONTACT PERSON: Telephone No. [REDACTED] Electronic mail [REDACTED]		
Protocol Amendment(s):  5. This amendment is issued to correct the "STUDY TITLE" on the previously issued project sheets. The correct information outlined above.			
[REDACTED]			

Date Issued: 07/12/17 [REDACTED]		Laboratory Project Identification No. 865-105 Zurex Pharma, Inc. Project No.: ZX-ZP-0073		
STUDY TITLE: Pivotal Clinical Evaluation of the Antimicrobial Effectiveness of Topically Applied ZuraPrep™		STUDY DIRECTOR: M. [name] CCRP  Signature [REDACTED] Date 07/12/17		
TEST AND CONTROL ARTICLES: ZuraPrep™ [REDACTED] ZuraPrep™ Vehicle (Without Isopropyl Alcohol) [REDACTED] ChloraPrep® [REDACTED] (Scrub Teal® Tint)		ID/LOT NO. [REDACTED]	DATE RECEIVED: [REDACTED]	DS NO. [REDACTED]
PERFORMING DEPARTMENT(S): Clinical Laboratory		STORAGE CONDITIONS: Location: [REDACTED]  Dark  Ambient Room Temperature  Desiccator   Freezer  Refrigerator  Other:		
CONDUCT OF STUDY:  FDA  EPA  R&D  GLP  GCP  Other:				
SPONSOR: Zurex Pharma, Inc. [REDACTED] Middleton, WI [REDACTED]		CONTACT PERSON: Telephone No. [REDACTED] Electronic mail [REDACTED]		
Protocol Amendment(s): 
6. This amendment is issued after the completion of testing to add additional efficacy criteria in the below sections to the study protocol [REDACTED]  [REDACTED]
 
 
The following paragraph is added to the end of Section 3.2 Primary Endpoint/Analysis and Section 6.1 Efficacy Parameters of the protocol:
 
 
Additionally, as recommended by FDA, product effectiveness will be measured using the average treatment effects (ATE). The ATE will be estimated from a linear regression of posttreatment bacterial count (<math>\log_{10}</math> scale) at 10 minutes on the additive effect of a treatment indicator and the baseline or pretreatment measurement (<math>\log_{10}</math> scale). To show effectiveness, the test product will be 1) non-inferior to ChloraPrep® with a 0.5 margin (<math>\log_{10}</math> scale, upper bound of 95% confidence interval of the difference in ATE values <math>\leq 0.5</math>) and 2) superior to the vehicle control by a margin of 1.2 (<math>\log_{10}</math> scale, lower bound of 95% confidence interval of the difference in ATE values <math>\geq 1.2</math>).
 
 
Section 3.2 Secondary Endpoints/Analysis and 6.1 Secondary Endpoints/Analysis is revised as follows (additions underlined for clarity):
 
 
Responder rates, ATE values, and differences in ATE values at 30 seconds will be calculated identically to the 10 minute responder rates and ATE values. At 6 hours a site is considered a responder if it is below baseline; otherwise, 6 hour responder rates will be calculated identically to the 10 minute responder rates. The secondary efficacy goals are to have the 95% confidence intervals for the responder rates to be greater than or equal to 70%. Log10 CFU reduction from baseline will also be calculated for all post-prep samples. The non-inferiority and superiority goals for ATE values are identical to those at 10 minutes.
				

Date Issued: 07/12/17 [REDACTED]

Laboratory Project Identification No. 865-105  
Zurex Pharma, Inc. Project No.: ZX-ZP-0073

**Protocol Amendment(s): (continued)**

- The following paragraphs are added to end of Section 8.2.1 Efficacy Analysis of the protocol:

Average Treatment Effect (ATE) will be estimated from a linear regression of posttreatment bacterial count ( $\log_{10}$  scale) on the additive effect of a treatment indicator and the baseline or pretreatment measurement ( $\log_{10}$  scale). ATE will be calculated for the 10 minute samples separately for each product and each body area. This will generate 3 (products) \* 2 (body areas) \* 1 (post-treatment time point) = 6 ATEs, one each for each combination of product and body area at 10 minutes. The ATEs will be compared as follows:

- a. ZuraPrep™ will be compared to the ChloraPrep®. To show effectiveness, ZuraPrep™ should be non-inferior to ChloraPrep® with a 0.5 margin. Specifically, the upper bound of the 95% confidence interval of the ATE of ChloraPrep® minus the ATE of ZuraPrep™ should be less than or equal to 0.5.
- b. ZuraPrep™ will be compared to ZuraPrep™ vehicle. To show effectiveness, ZuraPrep™ should be superior to ZuraPrep™ vehicle by a 1.2 margin. Specifically, the lower bound of the 95% confidence interval of the ATE of ZuraPrep™ minus the ATE of ZuraPrep™ vehicle should be greater than or equal to 1.2.

The same ATE calculations will be performed for the 30 second time point, but the results are for informational purposes only.

[REDACTED]

[REDACTED]

Date Issued: 10/26/17 [REDACTED]	Laboratory Project Identification No. 865-105 Zurex Pharma, Inc. Project No.: ZX-ZP-0073		
STUDY TITLE: Pivotal Clinical Evaluation of the Antimicrobial Effectiveness of Topically Applied ZuraPrep™	STUDY DIRECTOR: M. [name] CCRP Signature [REDACTED] Date 10/26/17		
TEST AND CONTROL ARTICLES: ZuraPrep™ [REDACTED] ZuraPrep™ Vehicle (Without Isopropyl Alcohol) [REDACTED] ChloraPrep® [REDACTED] (Scrub Teal® Tint)	ID/LOT NO. [REDACTED]	DATE RECEIVED: [REDACTED]	DS NO. [REDACTED]
PERFORMING DEPARTMENT(S): Clinical Laboratory	STORAGE CONDITIONS: Location: [REDACTED]  Dark  Ambient Room Temperature  Desiccator  Freezer  Refrigerator  Other		
CONDUCT OF STUDY:  FDA  EPA  R&D  GLP  GCP  Other:			
SPONSOR: Zurex Pharma, Inc. [REDACTED] Middleton, WI [REDACTED]	CONTACT PERSON: [REDACTED] Telephone No. [REDACTED] Electronic mail [REDACTED]		
Protocol Amendment(s):			
7. Section 5 on page 19 of the protocol references "E1173-01" for ASTM "Standard Test Method for Evaluation of Preoperative, Precatheterization, or Preinjection Skin Preparations", however the correct reference is E1173-15. This amendment is issued to correct the typographical error in the protocol.			
8. Section 13 on page 35 of the protocol provides an incorrect citation for "Standard Test Method for Evaluation of Preoperative, Precatheterization, or Preinjection Skin Preparations". The correct citation is "Annual Book of ASTM Standards Vol 11-08. E1173-15 "Standard Test Method for Evaluation of Preoperative, Precatheterization, or Preinjection Skin Preparations. This amendment is issued to correct the typographical error in the protocol.			
Protocol Deviation(s):			
1. Section 8.5.1 of "Procedure for Neutralization Validation" on page 51 of the protocol requires triplicate plating of the sterility controls, however, since duplicate plating was performed for all tests of this study, the sterility controls were also plated in duplicate. This deviation will not have any negative impact on the outcome of the study.			
[REDACTED]

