### 1.5 Study Population

Healthy male and female volunteers, 18 years of age or older, with no dermatological conditions or known history of sensitivity to natural rubber latex, adhesive skin products (e.g., Band-Aids, medical tapes), isopropyl alcohol or chlorhexidine gluconate will be enrolled into this study. For this trial, a sufficient number of volunteers will be recruited in the screening phase such that a total of at least 320 abdominal (sebaceous poor) regions and 320 groin (sebaceous rich) regions are evaluable at the completion of the study for the test article and reference article, and a total of at least 64 abdominal regions and 64 groin regions are evaluable at the completion of the study for the negative control. Subjects must satisfy all Screening Day and Treatment Day Inclusion/Exclusion Criteria prior to screening sample collection and Treatment Day procedures.

The right and left sides of both the abdomen and the groin must meet the minimum Screening Day baseline values stated in the Inclusion Criteria to qualify for the study.

At least 352 human subjects will be employed utilizing bilateral applications assuring that the treatments will be evaluated on the sites as described in the following table:

Table 1.5: Minimum number of readings per anatomical site (abdomen and groin), per treatment, per sampling interval (30 seconds, 10-minutes, and 6 hours post-application)		
Treatment	Number of Abdomen Evaluations	Number of Groin Evaluations
ZuraPrep™ [REDACTED]	320	320
ChloraPrep® [REDACTED], Scrub Teal® Tint (positive/active control)	320	320
ZuraPrep™ Vehicle, [REDACTED] (negative/inactive control)	64	64

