### 3. Study Design

#### 3.1 Study Type

This is a randomized, paired-comparisons design where each subject receives two of the planned treatments.

**Table 3.1:** Treatments, Anatomical Sites of Evaluation, Application and Dry Times and Coverage Areas (See Appendix 14.7 for detailed application instructions)

Treatment (Quantity/Volume)	Body Site	Application Time	Dry Time	Area of Coverage
ZuraPrep™ [REDACTED]	Abdomen (sebaceous poor)	30 seconds	3 minutes	5" x 5"
	Groin (sebaceous rich)	2 minutes	3 minutes	1.5" x 5"
ChloraPrep® [REDACTED] Scrub Teal® Tint, (positive control)	Abdomen (sebaceous poor)	30 seconds	3 minutes	5" x 5"
	Groin (sebaceous rich)	2 minutes	3 minutes	1.5" x 5"
ZuraPrep™ Vehicle, [REDACTED] (negative control)	Abdomen (sebaceous poor)	30seconds	3 minutes	5" x 5"
	Groin (sebaceous rich)	2 minutes	3 minutes	1.5" x 5"

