#### **4. Subject Selection**

Healthy volunteers with no dermatological conditions or known history of sensitivity to natural rubber latex, adhesive skin products (e.g., Band-Aids, medical tapes), isopropyl alcohol, citric acid, methylene blue, methylparaben, propylparaben, or chlorhexidine gluconate will be enrolled into this study. A sufficient number of volunteers will be enrolled in the screening phase such that the total number of abdominal regions and the total number of groin regions meets or exceeds the number determined for the study (320 abdominal regions and 320 groin regions for the test article and reference article; and 64 abdominal regions and 64 groin regions for the negative control). Subjects must satisfy all Screening Day and Treatment Day Inclusion/Exclusion Criteria prior to screening sample collection and Treatment Day procedures. Volunteers will be recruited and treated in blocks until the count of results in the mITT population meets or exceeds the required test material/region counts.

A subject must qualify for both the abdominal portion and the groin portion of the study. The right and left sides of the abdomen and groin must meet the minimum baseline values stated in the Inclusion Criteria.

Subjects who are treated but discovered to have Treatment Day baseline counts below the minimum values or above the maximum values stated in Table 3.2 will not be included in the primary efficacy analysis based on the body site(s) that did not qualify due to not meeting the treatment day baseline inclusion criteria - see section 4.1.

Subjects will be identified at screening by their initials and a screening ID number. Subject numbers will not be assigned until a subject has passed the screening criteria, including baseline bacterial counts.

All volunteers will be given verbal and written information about the study procedures, and Subject Instructions (Appendix 14.6) will be provided to each subject for the pretreatment

phase of the study. The following Inclusion/Exclusion Criteria will be reviewed on Screening Day and on Treatment Day to establish eligibility for participation:

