Two-sided confidence intervals for  $\log_{10}$  CFU/cm^2 changes from baseline will also be calculated. These calculations will use an ANOVA model with subject as a random variable and test substance as a fixed variable. Body area (abdomen or groin) will be a fixed variable. Sample times (30 seconds, 10 minutes, or 6 hours) will be calculated separately using identical models. Differences in  $\log_{10}$  CFU/cm^2 reductions will be calculated based on the same model.

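### The ATE regression and the log10 ANOVA default to one residual variance across products, with no provision for unequal variance, although vehicle has 64 readings against 320 per active product in each body area

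*Combined protocol and SAP*

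**What the plan says.** **ATE regression.** The addition that Amendment 6 makes to Section 8.2.1 reads: "Average Treatment Effect (ATE) will be estimated from a linear regression of posttreatment bacterial count", on the log10 scale, with a treatment indicator and the baseline count as additive terms. ATEs are reported "separately for each product and each body area", six in all at 10 minutes. Item b sets the criterion: "ZuraPrep™ should be superior to ZuraPrep™ vehicle by a 1.2 margin", judged on the lower 95% bound.

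**log10 ANOVA.** Section 8.2.1 says of the intervals for changes from baseline: "These calculations will use an ANOVA model with subject as a random variable and test substance as a fixed variable". Body area is a second fixed factor, and each sample time has its own model.

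**Group sizes and layout.** Section 1.5 requires, for the test and reference articles, "a total of at least 320 abdominal (sebaceous poor) regions and 320 groin (sebaceous rich) regions are evaluable", and "a total of at least 64 abdominal regions and 64 groin regions are evaluable at the completion of the study for the negative control". Section 4 repeats the vehicle figure. Section 3.1 describes a "randomized, paired-comparisons design where each subject receives two of the planned treatments".

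The visible text of neither analysis section gives a variance structure, a robust or Welch-type standard error, or a check of equal variance. No product's SD is shown.

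**The concern.** A single residual variance does little harm when groups are of similar size. Here the ratio is 5:1. The pooled estimate is then close to the active products' variance, while the sampling error of an active-minus-vehicle difference is mostly vehicle error. If vehicle readings vary more than active readings, the interval is too narrow and the lower bound passes 1.2 too easily. If they vary less, the interval is too wide and precision is lost.

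Unequal variance is plausible. Section 8.2.1 replaces zero plate counts by 0.5, which puts a floor under low counts and mainly affects products with a large kill. The comparison is between an alcohol product and the same formulation without alcohol. Neither fact shows which group is the more variable.

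The quantity most exposed is the 1.2 log10 superiority criterion. The 6-hour log10 comparison with vehicle (Section 3.2, Study Validity) uses the ANOVA and is exposed in the same way, though it has no numeric margin.

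**Working it through.** **Figures in the plan.** The layout adds up: 352 × 2 = 704 = 320 + 320 + 64 readings per body area. If every subject receives two different products, the only split that gives these totals is 288 subjects on ZuraPrep/ChloraPrep, 32 on ZuraPrep/vehicle and 32 on ChloraPrep/vehicle. The 267 per active treatment in Section 8.3 is approximately reproduced (70% against 77.8%, two-sided 0.05, 80% power: 269 with continuity correction; exact power at 267 is 82.1%), but it concerns responder rates and does not bear on this point. The minimum of 40 for vehicle cannot be rebuilt, because its inputs are not visible.

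**Inputs.** n = 320 per active product and 64 for vehicle (Section 1.5). Assumed: both active products have SD 1, and the vehicle SD is r, from 0.5 to 2.

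**Formulas (three-product fit, one body area).**
- Pooled variance: s² = (319 + 319 + 63r²)/701
- Model SE of ZuraPrep minus vehicle: √[s²(1/320 + 1/64)]
- Correct SE: √(1/320 + r²/64)
- Coverage: 2Φ(1.96 × model SE / correct SE) − 1
- One-sided error (the chance that the lower bound reaches 1.2 when the true difference is exactly 1.2): half of 1 − coverage, nominally 2.5%

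**Why the imbalance matters.** The actives carry 638/701 = 91% of the weight in s². Even at r = 1, vehicle supplies (1/64)/(1/64 + 1/320) = 83% of the variance of the difference.

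**Worked case, r = 1.5.** s² = (638 + 63 × 2.25)/701 = 1.112. Model SE = √(1.112 × 0.01875) = 0.144. Correct SE = √(0.003125 + 0.035156) = 0.196. The ratio is 0.74, so coverage is 85.2% and one-sided error 7.4%.

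**Range.** The simulated columns come from the paired 288/32/32 layout with ordinary three-product regression. Small differences from the formula are expected from simulation error and pairing.

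| r | Model SE / correct SE | Coverage, formula | One-sided error, formula | Coverage, simulated | One-sided error, simulated |
|---|---|---|---|---|---|
| 0.5 | 1.58 | 99.8% | 0.1% | 99.9% | about 0% |
| 0.75 | 1.23 | 98.4% | 0.8% | 99% | 0.4% |
| 1 | 1.00 | 95.0% | 2.5% | – | – |
| 1.25 | 0.85 | 90.3% | 4.9% | 91% | 4.6% |
| 1.5 | 0.74 | 85.2% | 7.4% | 85% | 7.7% |
| 2 | 0.60 | 76.2% | 11.9% | 77% | 11.6% |

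A regression on ZuraPrep and vehicle only, with s² = (319 + 63r²)/382, is similar: 86.8% coverage at r = 1.5 and 80.0% at r = 2.

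**Random-subject ANOVA.** This model pools both body areas, so per sample time it has 640 readings per active product and 128 for vehicle, still 5:1. Simulated with one residual variance and an assumed intraclass correlation of 0.2 to 0.5, coverage is 98.8% to 99.4% at r = 0.5, 87.6% to 89.8% at r = 1.5 and 79.7% to 82.4% at r = 2. The subject term lessens the problem without removing it.

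**Robust errors.** With HC3 or subject-clustered standard errors on the regression, simulated coverage is 94.1% to 95.8% and one-sided error 1.7% to 3.4% for every r from 0.5 to 2.

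**When the verdict would change.** With an active SD of 1 log10 (assumed) and r = 2, the reported half-width is 0.302 and the correct one 0.502. The criterion is then wrongly met only for estimates from 1.2 + 0.302 = 1.502 up to 1.2 + 0.502 = 1.702. At r = 0.5 the half-widths are 0.259 and 0.164, so estimates from 1.364 up to 1.459 would wrongly fail.

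**The case against.** **Pooling is not stated.** A reader might infer that the plan declares equal variances. It does not. It names two methods whose ordinary default is one residual variance. The phrase "separately for each product and each body area" could even suggest separate fits, but a treatment indicator cannot be estimated within one product, and separate fits would leave the interval for the difference undefined. Text near the decision rules is redacted, so a variance statement there cannot be excluded. This stands as a limit: the point concerns the visible text.

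**The trigger cannot be shown.** No SDs are visible, and the sponsor may hold them in the sample-size report (Appendix 14.12). A reader might infer that the 1.2 interval is too narrow and the superiority test too lenient. The documents do not support that. The floor could compress the active variance; site-to-site variation in kill could raise it. If vehicle is the less variable, the error is conservative. This also stands, and it is why the result is given as a range.

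**The consequence is limited.** The responder-rate goal uses exact intervals and is untouched. The ZuraPrep-ChloraPrep interval stays within 0.97 to 1.13 times its correct width for r from 0.5 to 2 if the two actives share a variance. A reader might treat the 6-hour vehicle comparison as another pass/fail bound, but the Study Validity text gives it no margin and places the superiority condition at the primary endpoint.

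What survives is that the default interval is fragile at 5:1, and that a better one costs almost nothing.

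**Conclusion.** The concern holds in conditional form. As visibly specified, both log10 analyses rest by default on one residual variance, and the 5:1 allocation makes vehicle contrasts sensitive to it. For assumed vehicle/active SD ratios from 0.5 to 2, nominal 95% coverage of the ZuraPrep-minus-vehicle interval runs from nearly 100% down to 76 to 77%, and one-sided error at the 1.2 margin from about 0% up to about 12%. The ANOVA is affected somewhat less.

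These sizes depend on assumed ratios, equal variance in the two active products, and the single-variance default actually being used. The documents do not establish that any interval is wrong, or in which direction. The improvement is worth making: Amendment 6 was issued once testing was finished, so an unstated standard-error method leaves an analytic choice open with the data already collected.

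**What to change.** Specify one method for each analysis, not a list of alternatives.

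- **Amendment 6, addition to Section 8.2.1:** state that 95% intervals for ATE differences use heteroscedasticity-robust standard errors clustered on subject, with a small-sample correction. Clustering is needed because each subject receives two products.
- **Section 8.2.1, log10 ANOVA:** keep the random subject term and estimate the residual variance separately for each product.
- Report the single-variance intervals only as a sensitivity analysis.

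Amendment 6 attributes the ATE approach to an FDA recommendation, and the visible text does not say whether that recommendation fixes the interval method, so the sponsor should confirm this. The change should be dated and justified in the final report, as Section 8.6 requires for departures from the statistical plan.

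The cost is one sentence in each place, with no new data or subjects. At equal variances almost nothing changes: with an active SD of 1, the simulated SE was 0.137 for ordinary regression, 0.138 for HC3 and 0.134 to 0.138 for clustered errors.
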